5.2 Prior Therapy Criteria

- a.** Prior neoadjuvant chemotherapy for this cancer is permitted however patients must have completed treatment within 70 days prior to cystectomy and recovered from all associated toxicities at the time of registration.
- b.** Patients must not have received any prior pelvic irradiation.
- c.** Patients must have no evidence of visceral or nodal metastatic disease proximal to the common iliac bifurcation on 2 view chest x-ray or CT of the chest and abdominal-pelvic imaging with computerized tomography or MRI of the abdomen and pelvis. Chest x-ray or CT of the chest and CT or MRI of the abdomen and pelvis must be obtained within 56 days prior to registration. PET/CT may be used as an alternative to CT or MRI or to resolve possible areas of metastases seen on cross sectional imaging.

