9.0 STUDY CALENDAR

REQUIRED STUDIES	PRE STUD Y	Hospitalization		Year 1				Year 2				Year 3				Year 4	Year 5	Year 6
		Day of Surgery	Day of Discharge	Mo	Mo	Mo	Mo	Mo	Mo	Mo	Mo	Mo	Mo	Mo	Mo	Mo	Mo	Mo
				3	6	9	12	15	18	21	24	27	30	33	36	48	60	72
PHYSICAL																		
History and Physical Exam	X ^a			X	X	X	X		X		X		X		X	X	X	X
Height, Weight and Performance Status	X																	
Hospitalization assessment ^b			X															
Adverse Event/Morbidity assessment ^c				X	X													
LABORATORY																		
Bilirubin	X			X	X	X	X		X		X		X		X	X	X	X
SGOT and SGPT	X			X	X	X	X		X		X		X		X	X	X	X
Alkaline Phosphatase ^d	X			X	X	X	X		X		X		X		X	X	X	X
STAGING																		
TURBT	X																	
Bimanual Exam	X																	
X-RAYS AND SCANS																		
CT or MRI of abdomen and pelvis	X				X		X		X		X		X		X	X	X	X
2 view Chest X-ray or CT of the Chest	X			X	X	X	X		X		X		X		X	X	X	X
Bone Scan, PET/CT or other imaging directed at potential visceral or node metastatic sites	X ^d																	
SPECIMEN SUBMISSION																		
Two Paraffin Embedded Blocks or 10 unstained slides from Primary Tumor		X ^e																
8 unstained, formalin-fixed paraffin embedded (FFPE) sections from the left-pelvic and right-pelvic lymph nodes		X ^e																

Calendar continued on next page. Click here for [footnotes](#).

TREATMENT (see Section 7.0 for details)														
Surgical assessment of nodal dissection ^f		X												
Standard or Extended Pelvic Lymph Node Dissection		X												
Submission of Materials for Surgical Review ^g		X												
Adjuvant chemotherapy ^h				X										

NOTE: Forms are found on the protocol abstract page of the SWOG website (www.swog.org). Forms submission guidelines are found in [Section 14.0](#).

- a Physical exam and medical history must be completed within 28 days prior to registration (see [Section 5.3b](#)).
- b See [S1011](#) Surgeons Post-Op Data Form (see protocol abstract page, www.swog.org).
- c Morbidity data **collected** on both [S1011](#) Surgeon's Post-Op Data Form Standard Versus Extended LND and [S1011](#) Surgeon's 90-Day Assessment Form Standard Versus Extended IND (see protocol abstract page, www.swog.org).
- d Bone scan required if patient has an elevated alkaline phosphatase or bone pain.
- e For patients who consent to specimen banking, specimens must be collected after completion of the final pathologic evaluation.

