In some cases, there may be a combination of markers that have a multiplicative effect on the risk of relapse or death. In addition to assessing multivariate proportional hazards regression models, we will also develop classification and regression trees to assess these potential multiplicative effects among the markers.

Although statistical power is lower, we also would like to evaluate whether some tissue markers are predictive of DFS and survival in those who receive neoadjuvant chemotherapy compared to those who did not. In other words, we will evaluate the marker by chemotherapy interaction, at least in a preliminary fashion. If we assume the following distribution of a tissue marker and neoadjuvant chemotherapy:

Tissue Marker Status (30% prev.)	Prior chemotherapy	Exposure to chemotherapy	Neoadjuvant
Yes			No
Absent	35%	HR = .48	35% HR = 1.0
Present	15%		15%

(and assume 55% 3-year DFS for those without the marker) and we specify a two-sided alpha=0.05 then there will be 80% statistical power to detect a difference in DFS hazard ratios of 1.0 for the tissue marker absence vs. presence in those without neoadjuvant chemotherapy versus a HR = 0.48 for the tissue marker absence vs. presence in those with prior chemotherapy, suggesting a predictive tissue marker for chemotherapy resistance.

This analysis assumes that type of nodal surgery does not have an impact, and the randomized groups are pooled together.

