14.4 Data Submission Overview and Timepoints

- a. WITHIN 7 DAYS OF STEP 1, REGISTRATION:

Submit the following:

S1011 Prestudy Form

Operative Report from TURBT

Pathology Report from TURBT

Radiology reports from cross-sectional imaging performed to determine the pre-REG clinical T stage, e.g. CT, MRI, or PET/CT.

- b. WITHIN 14 DAYS OF SURGERY, FOR ALL PATIENTS RECEIVING ON-STUDY SURGERY:

Submit copies of the following:

S1011 Intra-Op Surgical Assessment Form Standard Versus Extended LND

Intra-Op Photos

(Note: The Photo Upload Form is located in the data submission section of the SWOG CRA Workbench in the **S1011** Reg 2 folder under the 'Follow Up' tab. Photos should be obtained after the randomization and surgical assessment).

Operative Report from cystectomy

Pathology Report from cystectomy

- c. IF PATIENT CONSENTED, WITHIN 28 DAYS OF RANDOMIZATION:

Submit specimens as outlined in [Section 15.0](#).

- d. IF PATIENT NOT ELIGIBLE OR NOT CONTINUING TO STEP 2 RANDOMIZATION, WITHIN 14 DAYS AFTER GOING OFF STUDY:

S1011 Pre-Randomization Off Study Form

S1011 Intra-Op Surgical Assessment Form Standard Versus Extended LND
(Note: No Intra-Op photos are required for patients not going on to Step 2, Randomization)

e. WITHIN 7 DAYS FROM HOSPITAL DISCHARGE:

S1011 Surgeon's Post-Op Data Form Standard Versus Extended LND

S1011 Adverse Event Form

f. WITHIN 90 DAYS POST-SURGERY

S1011 Surgeon's 90-Day Assessment Form Standard Versus Extended LND

S1011 Adverse Event Form

g. AFTER SURGERY, EVERY THREE MONTHS FOR YEAR ONE; EVERY SIX MONTHS FOR YEARS TWO AND THREE; AND ANNUALLY UNTIL SIX YEARS AFTER RANDOMIZATION OR UNTIL DEATH:

Submit copies of the **S1011** Follow Up Form
(via the Medidata Rave® clinical data management system)

h. WITHIN 4 WEEKS OF KNOWLEDGE OF DEATH:

Submit the Notice of Death **and a final S1011** Follow Up Form.
(via the Medidata Rave® clinical data management system)

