15.1 Specimen Submission Timepoints

With patient's consent, specimens must be submitted at the following times (see [Section 9.0](#)):

Within 28 days of randomization, submit:

- a. Two paraffin embedded blocks (preferred) or 10 unstained slides from the primary tumor (allowed, if the primary tumor blocks will not be released) AND a copy of the pathology report
- b. Eight unstained, 4-micrometer (μ m), formalin-fixed, paraffin-embedded (FFPE) sections from the "left pelvic" and "right pelvic" lymph node packets

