The goal of this correlative study is to explore the role of epithelial-mesenchymal transition in the process of metastases and disease progression for patients undergoing radical cystectomy for bladder cancer.

2. Specific hypotheses:

Hypothesis: Epithelial-mesenchymal transition drives lymph node metastasis and systemic circulation of tumor cells in patients with muscle invasive bladder cancer.

Aim a: To identify the relationship between expression of markers of epithelial-mesenchymal transition in the primary bladder tumor with local tumor stage, the burden of lymph node metastases, and the likelihood of disease progression among patients undergoing cystectomy for muscle invasive bladder cancer.

Aim b: To correlate the expression of markers of epithelial-mesenchymal transition in primary bladder tumors.

3. Methods and specimen collection

Sample collection:

After the patient has consented to the **S1011** trial, radical cystectomy with lymph node dissection will be performed in a carefully controlled fashion per study protocol. Bladder and nodal specimens will be fixed in formalin and paraffin embedded according to a study prescribed protocol. Two paraffin embedded blocks representative of the primary tumor will be sent to the SWOG biorepository, where tissues will be used for tissue microarrays and allocated for RNA extraction. (See [Section 15.0](#))

Immunohistochemistry protocol:

The following well-characterized antibodies and corresponding final working concentrations will be used for this study: E-Cadherin, mAb, Zymed, Cat# 13-1700, 1:1000, Twist, rabbit poly Ab, Santa Cruz

Biotechnology, clone H81, dilution 1:50; EGFR, mAb, Zymed 28-005, dilution 1:10; Ki67 (MIB-1), mAb, DAKO, M7240, dilution 1:2000; P53 (AB-2), mAb, calbiochem, #0P09L, dilution 1:500; P63(4A4), mAb, Santa Cruz, # sc-8431, dilution 1:500; pAKT(ser 473), rabbit poly, cell Signaling, # 3787L, dilution 1:50; PTEN mAb, Cascade, ABM-2052, dilution 1:75; RB, mAb, QED, #3101-31-7, dilution 1:1000.

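### The exploratory marker-by-neoadjuvant-chemotherapy interaction uses cystectomy tissue, which is post-treatment residual tumor in one group and chemotherapy-naive tumor in the other, so it cannot be read as identifying a marker of chemotherapy resistance.

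*Combined protocol and SAP*

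**What the plan says.** **Tissue source.** The study calendar (9.0) lists "Two Paraffin Embedded Blocks or 10 unstained slides from Primary Tumor" under the day of surgery only. Section 15.1 opens with "Within 28 days of randomization, submit" and asks for "Two paraffin embedded blocks (preferred) or 10 unstained slides from the primary tumor"; randomization takes place during the operation (7.1). Appendix 18.2, part a.3, describes tissue from the on-study cystectomy: "Bladder and nodal specimens will be fixed in formalin and paraffin embedded according to a study prescribed protocol". It continues: "Two paraffin embedded blocks representative of the primary tumor will be sent to the SWOG biorepository, where tissues will be used for tissue microarrays".

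**Diagnostic resection.** TURBT is a required pre-study item in 9.0, and histologic proof is an entry criterion (5.1a). Section 14.4a asks for reports from that procedure, such as the "Pathology Report from TURBT", but no tissue.

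**Chemotherapy timing.** Under 5.2a, "patients must have completed treatment within 70 days prior to cystectomy".

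**Analysis.** Section 11.4 assumes that 70% of patients have adequate tissue, giving 396 samples. It plans three analyses involving chemotherapy:
- a chi-square test of marker expression against neoadjuvant exposure;
- outcome analyses repeated by neoadjuvant and adjuvant chemotherapy, with interaction tests aimed at chemoresistance;
- a powered marker-by-neoadjuvant interaction on DFS, described as preliminary, with 30% marker prevalence in both exposure groups. A positive result is described as "suggesting a predictive tissue marker for chemotherapy resistance".

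**Scoring.** Immunohistochemistry is recorded as the percentage of tumor cells staining and the intensity of staining (18.2, a.3). The documents do not discuss pre-treatment marker status or patients without residual tumor.

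**The concern.** A marker that predicts resistance has to be measured before the treatment it is meant to predict. Here that holds in only one of the two groups compared.

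1. **Measurement after exposure.** In treated patients the marker is read in cells that survived chemotherapy, which may have selected those cells or changed their expression. In untreated patients it is read in tumor never exposed to chemotherapy. Equal prevalence in the two groups, which 11.4 assumes, need not hold.
2. **Selection on response.** A treated patient with no tumor left in the bladder has nothing to score. The best responders leave the treated group because they responded, so missingness depends on the outcome the marker is supposed to predict. Some untreated patients may also have no tumor left after TURBT, but loss through response to chemotherapy occurs only in the treated group.

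At stake is the stated conclusion of one exploratory analysis. A real chemosensitivity marker could be weakened or missed, and whatever difference appears could not be attributed to resistance. A larger sample does not correct either problem.

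**Working it through.** **Step 1. Reproduce the plan's figures.** Inputs from 11.4: 70% tissue availability; cells of 35%, 15%, 35% and 15%; 55% three-year DFS without the marker; hazard ratio (absent vs present) 0.48 with prior chemotherapy and 1.0 without; two-sided alpha 0.05. The 5-year accrual plus 3-year follow-up is stated for the main-effect table and is assumed here to apply to the interaction.

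- Samples: 0.70 × 564 = 394.8, or 197.4 per arm. Rounded up to 198 per arm, this gives 396.
- Hazard: λ = −ln(0.55)/3 = 0.199 per year; in the treated, marker-present cell, λ/0.48 = 0.415.
- Event probability with uniform accrual: 1 − (e^(−3λ) − e^(−8λ))/(5λ) = 0.652 and 0.879 respectively.
- Expected events: 396 × 0.35 × 0.652 = 90.3 (marker absent, in each exposure group); 396 × 0.15 × 0.879 = 52.2 (treated, present); 396 × 0.15 × 0.652 = 38.7 (untreated, present).
- Standard error of the log ratio of hazard ratios: √(1/90.3 + 1/52.2 + 1/90.3 + 1/38.7) = 0.259.
- Power: Φ(|ln 0.48|/0.259 − 1.96) = 80.9%, against the stated 80%.

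The arithmetic in 11.4 is sound on its own assumptions.

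**Step 2. Loss of unscorable treated patients.** The documents give no rate, so 10–40% of the treated half is assumed. In one version the loss is independent of the marker (both treated cells scaled by 1 − c). In the other only marker-absent patients are lost (treated absent cell = 0.35 − 0.5c, so prevalence among treated residual tumors = 0.15/(0.50 − 0.5c)).

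| Assumed loss c | Samples left | Power, loss independent of marker | Power, only marker-absent lost | Marker prevalence in treated residual tumors, only marker-absent lost |
|---|---|---|---|---|
| 0 | 396 | 80.9% | 80.9% | 30% |
| 10% | 376 | 78.9% | 79.8% | 33% |
| 20% | 356 | 76.6% | 78.3% | 38% |
| 30% | 337 | 73.7% | 76.2% | 43% |
| 40% | 317 | 70.0% | 72.7% | 50% |

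These losses apply only if the 70% tissue rate does not already include such patients.

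**Step 3. Bias in the treated group.** All inputs are assumed except the 30% prevalence: complete response in 40% of marker-absent and 10% of marker-present patients; hazard 0.06 per year after complete response and 0.28 per year with residual tumor. DFS in each marker group is then p·e^(−0.06t) + (1 − p)·e^(−0.28t), with p = 0.40 or 0.10. The large-sample Cox hazard ratio (absent vs present) was solved numerically under the accrual and follow-up of Step 1. Let k be the factor by which the residual-tumor hazard is higher when the marker is present. Among residual tumors the hazard ratio is then exactly 1/k.

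| k | HR, all treated | HR, residual tumor only |
|---|---|---|
| 1.0 (acts only through complete response) | 0.68 | 1.00 |
| 1.3 | 0.54 | 1/1.3 = 0.77 |
| 1.5 | 0.48 | 1/1.5 = 0.67 |

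The first row is 1.00 by construction, because such a marker has no effect once complete responders are removed. The other rows show attenuation. Step 3 covers selection only. The effect of chemotherapy on expression itself cannot be quantified, or its direction given, from the documents.

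**The case against.** The strongest case against has five parts.

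- **Purpose is modest.** The interaction is labeled preliminary, specimens are optional, the assays await funding (15.0), and the EMT aims in 18.2 concern stage, nodal burden and progression. This stands, and it limits the importance of the point. But the label excuses low power; it does not justify a stated interpretation that the tissue cannot support.
- **Other analyses are sound.** A reader might infer that the plan cannot study chemoresistance at all. The documents do not support that: 11.4 also tests interaction with adjuvant chemotherapy, and cystectomy tissue predates that treatment. A reader might also extend the fault to the chi-square test of expression against neoadjuvant exposure. That test asks whether expression differs after exposure, carries no resistance reading, and suits post-treatment tissue, though it is limited to residual disease. On TURBT tissue it would show only who was selected for chemotherapy.
- **The vanishing signal is an extreme case.** This stands. Step 3 shows attenuation under milder mechanisms, and every response rate and hazard in it is assumed.
- **Power loss may be counted twice.** This stands as a caveat, since the 70% figure may already include patients without tumor. Even so, 11.4 applies it without regard to exposure or response, and the treated group would still lack its best responders.
- **TURBT tissue is not expressly barred.** Section 15.1 says only primary tumor, and the detailed instructions cited in 15.2 are on a web page not included here. The calendar and appendix nonetheless point to cystectomy, and no provision sends both exposure groups to pre-treatment tissue.

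**Conclusion.** The point holds for the neoadjuvant interaction in 11.4 and its resistance reading, and for nothing else. The treated group supplies post-chemotherapy residual tumor, the untreated group supplies chemotherapy-naive tumor, and treated patients without residual tumor cannot be scored. That last step is an inference from the tumor-cell scoring rule; the documents do not state it. A difference between the groups would describe prognosis given residual tumor, not prediction from a baseline marker.

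The selection may attenuate a true signal (0.54 to 0.77, or 0.48 to 0.67, in the illustrations). It removes the signal only if the marker acts wholly through complete response (0.68 to 1.00). The power effect is secondary: from 80.9% to between 70.0% and 76.6% at assumed losses of 20–40% independent of the marker, subject to the caveat on the 70% tissue rate. The 80% in 11.4 is not an arithmetic error.

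The adjuvant interaction, the expression-by-exposure comparison, the other EMT aims and the primary DFS analysis do not share the fault.

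**What to change.** - **Specimens (9.0, 15.1a, 18.2 a.3).** Request archived pre-chemotherapy TURBT blocks or unstained slides, where consent and release allow, from consenting patients in both exposure groups. State explicitly which specimen each submission refers to. Keep the cystectomy block where tumor remains.
- **Analysis (11.4).** Run only the neoadjuvant interaction on TURBT tissue, in both groups. Keep cystectomy tissue for the expression-by-exposure comparison, the adjuvant interaction and the other aims.
- **Where TURBT tissue is unavailable.** Report the neoadjuvant interaction as prognosis given residual tumor, drop the chemoresistance reading, and report how many treated patients had no scorable tumor.
- **Limits to state in either case.** Entry and the start of DFS follow chemotherapy, so patients who progressed or became unfit for surgery during it never appear. The result is conditional on reaching randomization, and chemotherapy was not randomized. TURBT tissue restores the complete responders but not these patients.

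**Cost.** No new procedure or visit is needed, because TURBT is already required before entry. The document is marked closed effective 04/15/2017, so for enrolled patients this means retrospective retrieval. Some blocks will be small or not released, and whether consent covers TURBT tissue must be checked. The relabeling alone needs only a short change to 11.4.

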Several correlative studies have been built into the original protocol. The statistical considerations for the current study are slightly different, as we plan to incorporate a testing and validation cohort. We expect that 395 patients will have usable lymph node samples as specified in the protocol (assuming that tissue is available for 70% of study participants). The testing cohort will be comprised of the first half of these patients, or approximately 200 patients, and the results from the second 200 patients will be used for validating the results. On a case by case basis, some patients who are found to be ineligible for the clinical trial due to reasons other than pathology may be used for these analyses.

The underlying hypothesis for the correlative studies associated with this aim is that biomarker expression levels (i.e., (CD15, pSTAT3, VEGFR1 and CD68 cell counts in the benign nodal tissue) may predict clinical outcome (i.e., DFS). For each biomarker, recursive partitioning will be used to determine the cutoff value of average cell count that maximally distinguishes DFS within the training cohort. These cutoffs will be examined in the validation cohort.

[Table 1](#) provides an estimate of the minimally detectable hazard ratio for DFS for those with an elevated biomarker expression level (i.e., high CD15

	Prevalence of "High" Biomarker Expression Level				
	10%	20%	30%	40%	50%
DFS HR	2.40	1.93	1.80	1.74	1.73

Table 1. Minimally detectable hazard ratio (HR) for DFS for those with "high" biomarker expression versus those with "low" biomarker expression. Assuming 80% statistical power, 2-sided alpha of 0.05, and 200 patients in the training set (same power for the 200 patients in the validation set).

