expression) relative those with a low biomarker expression level. These effect sizes apply equally to the training and validation subsets since the sample size will be the same for both. The designation of "high" and "low" biomarker expression levels will be based on the cutoffs designated in the training cohort. These calculations assume 5 years of accrual, 3 additional years of follow-up, median 3-year DFS of 50% in those with "high" biomarker expression, a two-sided alpha of 0.05, and 80% statistical power. These calculations further assume that there is no interaction between the marker of interest and the randomized treatment assignment (type of lymph node dissection). Because all currently enrolling patients are being offered participation in the banking of their lymph node tissue, there will be no loss of sample size for this recently activated trial.

In some cases, there may be a combination of biomarkers that have a multiplicative effect on the risk of relapse. Classification and regression trees to assess the potential multiplicative effect amongst markers and form prognostic groups based on these algorithms will be explored. Prognostic models using traditional clinical factors such as clinical stage,

pathologic stage, age, receipt of neoadjuvant chemotherapy and performance status to predict disease-free survival will be developed in the training set and the area under the curve (AUC) will be calculated in the validation set. (43) Then, the model that also incorporates markers of the pre-metastatic niche (identified in the training set) will also be added to the model and the AUC will again be estimated. A comparison of the traditional AUC to the niche AUC will be made to evaluate whether these biomarker expression factors contribute to the DFS prognosis in this patient population.

Bibliography for 18.2

- 1 Fidler, I.J., Critical factors in the biology of human cancer metastasis: twenty-eighth G.H.A. Clowes memorial award lecture. *Cancer Res* 50(19):6130-8, 1990.)

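### Appendix 18.2b Table 1 gives training and validation the same 80% power because N is equal, with no allowance for a cutoff that is estimated in one half and tested in the other

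*Combined protocol and SAP*

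**What the plan says.** Appendix 18.2b, Statistical Plan, divides about 395 usable lymph node samples by order: the first half trains, the second half validates. For each of the four markers (CD15, pSTAT3, VEGFR1, CD68), "recursive partitioning will be used to determine the cutoff value of average cell count that maximally distinguishes DFS within the training cohort". The next step is stated briefly: "These cutoffs will be examined in the validation cohort".

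Table 1 then gives minimally detectable DFS hazard ratios of 2.40, 1.93, 1.80, 1.74 and 1.73 for a high-expression prevalence of 10, 20, 30, 40 and 50%. Its caption sets power at 80% and two-sided alpha at 0.05, for "200 patients in the training set (same power for the 200 patients in the validation set". The text below the table gives the reason: "These effect sizes apply equally to the training and validation subsets since the sample size will be the same for both". It also says that the high and low "biomarker expression levels will be based on the cutoffs designated in the training cohort".

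The plan gives no minimum node size, no marker distribution and no form for the relation between marker and risk.

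**The concern.** Equal sample size gives equal power only if the same test is run in both halves. Here one half searches for the cutoff and the other tests what the search returned. In training, the log-rank statistic is the largest over many candidate cutoffs, so a nominal 0.05 test of it has neither the stated alpha nor the stated power. In validation, the test is sound, but the cutoff carried into it may be misplaced. Patients then fall into the wrong group and the high/low contrast shrinks. Table 1 reflects neither effect.

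At stake is the interpretation of translational objective 1.3b, the prognostic value of these markers. Someone who trusts 80% would expect a real marker of the listed size to miss significance in validation one time in five. Under some plausible marker-risk relations it would miss about one time in three.

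**Working it through.** **Inputs from Appendix 18.2b.** 200 patients per half, two-sided alpha 0.05, 5 years of accrual plus 3 of follow-up, 50% DFS at 3 years in the high group, and the printed hazard ratios (HR).

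**Step 1: the plan's own figure, cutoff known.** Hazard in the high group λ_H = ln 2/3 = 0.231 per year; in the low group λ_L = λ_H/HR. With uniform accrual over A = 5 years and follow-up F = 3 years, the event probability is

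P(λ) = 1 − [exp(−λF) − exp(−λ(A+F))]/(λA).

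P(λ_H) = 0.7035. At prevalence p, the expected events are e_H = 200·p·P(λ_H) and e_L = 200·(1−p)·P(λ_L). Power = Φ(ln HR/√(1/e_H + 1/e_L) − 1.96).

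| Prevalence | HR | P(λ_L) | e_H | e_L | ln HR / SE | Power |
|---|---|---|---|---|---|---|
| 10% | 2.40 | 0.405 | 14.1 | 73.0 | 3.01 | 85% |
| 20% | 1.93 | 0.475 | 28.1 | 75.9 | 2.98 | 85% |
| 30% | 1.80 | 0.498 | 42.2 | 69.7 | 3.01 | 85% |
| 40% | 1.74 | 0.509 | 56.3 | 61.1 | 3.00 | 85% |
| 50% | 1.73 | 0.511 | 70.4 | 51.1 | 2.98 | 85% |

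The Lachin-Foulkes formula gives 83-84%, and log-rank simulation gives 82-85%. The printed row is therefore slightly conservative for a known cutoff. With 2 instead of 3 years of follow-up, the formula above returns 2.38/1.93/1.79/1.74/1.73 at 80% power, almost exactly the printed row. So Table 1 behaves as a fixed-cutoff calculation with no term for choosing the cutoff.

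**Step 2: cutoff estimated, step effect (assumed).** Simulate 200 training and 200 validation patients with the Step 1 hazards and the printed HR at a true change point. Choose the training cutoff with the largest log-rank statistic, subject to a minimum group size, and apply it unchanged to the validation patients with a two-sided 0.05 log-rank test.

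| Setting | Validation power |
|---|---|
| Cutoff known | 82-85% |
| Minimum group 10% of patients | 60/67/69/68/68% at prevalence 10/20/30/40/50% |
| Minimum group 5% | 63-67% |
| No minimum | 53-55% |
| Minimum group 20% | 64-73% at prevalence 20-50%; about 30% at prevalence 10% |

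These runs give both halves the same follow-up. With sequential halves (validation follow-up 3 to 5.5 years), the known-cutoff power is 78-80% and the estimated-cutoff power 60-65%.

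**Step 3: the training half.** In the step model with a 5-10% minimum group, the optimised training statistic exceeds 1.96 in 90-97% of replicates, while the same cutoffs succeed in validation in roughly 60-69%. The 90-97% is not genuine power, because the search also raises the false-positive rate. It shows only that the halves are not interchangeable.

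**Step 4: smooth effect (assumed).** With risk log-linear in the marker, scaled so that a median split has about 85% power, the estimated cutoff gives about 77-80% in validation.

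**Step 5: hazard ratios for 80% validation power, step model.** A grid search with minimum group sizes of 5-10% gives roughly 2.9-3.1, 2.15, 2.0, 1.9 and 1.9 at prevalence 10, 20, 30, 40 and 50%.

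**The case against.** The strongest reply is that the plan defines high and low by the training cutoff. Once training is finished the cutoff is fixed, and the validation test is an ordinary two-group log-rank on independent patients. If the printed HR and prevalence hold between those designated groups, power is about 80% or slightly more. This stands as a reading. It does not rescue the table, because the HR and prevalence at a data-chosen cutoff are unknown at design, so Table 1 could not then say which marker is detectable. Nor does it rescue the training claim.

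Second, the documents specify neither a step effect nor a minimum group. The markers are average cell counts, and the pilot data describe a broad range of staining, so a step is not an obvious default. A smooth effect loses only about 5 to 8 points. This stands in full: any single power figure has to carry its assumptions.

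Third, the consequences are limited. An AUC comparison is also planned in the validation set, so the log-rank test is not the only check there. Nothing says that a non-significant result will count against a marker. Section 15.0 makes the translational work conditional on funding, and Table 1 is offered as an estimate. All of this is correct, and it keeps the point minor.

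**Conclusion.** The equal-power statement does not hold, and Table 1 makes no allowance for estimating the cutoff. Those two conclusions need no assumption about the marker.

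The size of the loss does need one. For a true step at the printed HR, with 5 + 3 years, median DFS of 3 years in the high group and a smallest group of about 5-10%, validation power is about 60-69% against 82-85% with a known cutoff. Other minimum sizes give about 53-73%, falling to about 30% at 10% prevalence with a 20% minimum. A smooth effect gives about 77-80% against about 85%.

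A reader might infer that validation power simply is 60-69%, or that the Table 1 arithmetic is wrong. The documents support neither. The first figure rests on a step effect and a node size that the plan never states, and the printed hazard ratios are adequate for a cutoff fixed beforehand. What fails is the claim about where they apply.

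**What to change.** In Appendix 18.2b:

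- State that Table 1 holds only for a cutoff fixed independently of the patients being tested, with the printed HR and prevalence holding between the groups that the cutoff produces.
- Delete the caption's statement of equal power in validation and the sentence "These effect sizes apply equally to the training and validation subsets since the sample size will be the same for both".
- Do not claim 80% power at alpha 0.05 for the training half, where the cutoff is optimised. Cutting the caption back to training alone would leave the wrong half named.
- Prespecify the minimum node size for the recursive partitioning.
- Add simulated validation power with its assumptions beside it: about 60-69% for a step effect, where 80% needs HRs of roughly 2.9-3.1/2.15/2.0/1.9/1.9, and about 77-80% for a smooth effect. Rerun the simulation once the node size is set, and use the sequential split.
- Report a marker that misses significance in validation with its HR and confidence interval, as not confirmed.

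The cost is wording and a short simulation, with no added patients or samples. The downside is a less favourable stated power. The primary DFS analysis and the trial's sample size do not change.
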